The study plan will include five visits in total. An Early Termination (ET) visit will be performed in case of treatment discontinuation.

The patients will be assessed at Screening (Visit -1, Day -5/-3), Baseline (Visit 0, Day 0-Week 0), and at Week 8 (Visit 1), Week 12 (Visit 2) and Week 24 (Visit 3). A \pm 3-day window is allowed for the planned days of the visits.

Clinical assessments and cognitive impairment (EDSS, 25-foot Timed Walk [25WFT]; 9 Hole PEG Test [9HPT]; SDT; Low Contrast Letter Acuity test; MFIS and FSS) will be performed in all patients at screening (Visit -1, Day -5/-3), baseline (Visit 0, Day 0-Week 0), and at Week 8 (Visit 1), Week 12 (Visit 2) and Week 24 (Visit 3) from the first day of treatment with D-asp/placebo, as well as at the ET visit in case of treatment discontinuation. In the case of occurrence of a relapse, clinical assessments will be recorded during the inpatient ward access by neurologist's experts in the diagnosis and treatment of MS.

Neurophysiological assessments (LTP and recruitment curve) will be performed at the centre of the PPD only in patients without relapse, at baseline (Visit 0, Day 0-Week 0), and at Week 8 (Visit 1), Week 12 (Visit 2) and Week 24 (Visit 3) from the first day of treatment with D-asp/placebo, as well as at the ET visit in case of treatment discontinuation.

Immune-phenotype and immunometabolic analysis will be performed in patients enrolled in the centres of Rome, Naples and Pozzilli in samples obtained at baseline (Visit 0, Day 0-Week 0) before receiving corticosteroids, and after 8 (Visit 1) and 12 (Visit 2) weeks from the first day of treatment with D-asp/placebo, as well as at the ET visit in case of treatment discontinuation.

Brain MRI will be performed according to local clinical practice at screening (Visit -1, Day -5/-3), baseline (Visit 0, Day 0-Week 0) or previous MRI will be evaluated if available and 24 (Visit 3) weeks from the first day of treatment with D-asp/placebo, as well as at the ET visit in case of treatment discontinuation, whenever it will be available.

Adherence to treatment will be assessed after 8 (Visit 1), 12 (Visit 2) and 24 (Visit 3) weeks from the first day of treatment with D-asp/placebo, as well as at the ET visit in case of treatment discontinuation.

The occurrence of adverse events (AEs) will be monitored over the total study duration.

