Therefore, each potentially eligible patient will be informed of the study's objectives and overall requirements. Before conducting any of the pre-entry tests not performed routinely in the patient's treatment, the Investigator will explain the study fully to the patient using the Informed Consent Form. If the patient is willing to participate in the study, he/she will be requested to give written informed consent after being given sufficient time to consider his/her participation and the opportunity to ask for further details. The Informed Consent Form will be signed and personally dated by both the patient and the Investigator/Co-Investigator. A copy of the signed form will be provided to the patient and the original will be retained with the source documents. Although nursing staff may be involved in describing the study to a patient, the Investigator/Co-Investigator must participate in discussions with the patient and must sign and personally date the Informed Consent Form.

Patients that will take part in the Neurophysiological assessments (patients without relapse enrolled in the centre of [PPD](#) [REDACTED]) and in the immune-phenotype and immunometabolic analysis (patients enrolled in the centres of Rome, Naples and Pozzilli) will sign a further specific Informed Consent Form.

A screening log will be completed for all patients who sign the Informed Consent Form but do not subsequently enter the study. Patients will be identified by their initials and dates of birth; in addition, each patient's gender and reasons for exclusion from the study will be recorded.

Patients meeting the eligibility criteria during the 3-5 days of Screening period will be assessed at baseline (Visit 0, Day 0-Week 0), and after 8 (Visit 1), 12 (Visit 2) and 24 (Visit 3) weeks from the first day of treatment with D-asp/placebo. The Baseline visit (Visit 0) will take place within 3-5 days from the screening visit (Visit -1). A \pm 3-day window is allowed for the planned days of the post-baseline visits.

An ET visit will be arranged for the patients that withdraw from the study at any time: they will undergo all assessments requested at the ET Visit as soon as possible after the study discontinuation.

Screening Period (Visit -1, Day -5/-3)

A complete pre-study evaluation (Screening visit, Visit -1) will be performed within 3-5 days prior to Baseline to include:

- Written Informed Consent prior to conducting any protocol assessments;
- Demographics data;

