8.4.2 Analysis of Primary Endpoint

The comparison between the proportions of recoveries at 8 weeks in patients treated with D-aspartate and patients treated with placebo will be based on descriptive statistics (difference, relative risk and/or odds ratio) and on the chi-square test.

A set of exploratory analyses is planned. First, a multiple logistic regression model will be fitted to the data with recovery at 8 weeks as the dependent variable and age, sex, current DMT use, disease course, severity of relapse, and random assignment as covariates, to adjust for imbalances between the treatment groups.

Second, the time to recovery will be computed for each patient and included as the dependent variable in a multivariate Cox model, with all the above mentioned variables as covariates. Patients not recovered will be censored at last observation.

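### The exploratory Cox model treats time to recovery as an exact, right-censored time, but the visit schedule shows only the interval in which recovery occurred

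*Combined protocol and SAP*

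**What the plan says.** Section 8.4.2 makes the chi-square test of recovery at 8 weeks the main analysis. It then announces further work: "A set of exploratory analyses is planned". The second item is the Cox model, in which "the time to recovery will be computed for each patient and included as the dependent variable in a multivariate Cox model", using the same covariates as the logistic model. The only censoring rule is "Patients not recovered will be censored at last observation". The section gives no time origin, no rule for dating a recovery, no tie method and no treatment of interval censoring.

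Section 5.1 fixes when disability is scored: at screening, at baseline, "and at Week 8 (Visit 1), Week 12 (Visit 2) and Week 24 (Visit 3) from the first day of treatment with D-asp/placebo", and "as well as at the ET visit in case of treatment discontinuation". It adds that a ± "3-day window is allowed for the planned days of the visits"; Section 7.1 says the same of the post-baseline visits. Table 1 schedules no EDSS between baseline and Week 8, and the documents describe no diary or other record of a recovery date.

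The time origin is open. Section 5.1 counts visits from first treatment, whereas Section 5.2 speaks of recovery 8 weeks after relapse onset. Section 5.3.1 allows onset up to 5 days before inclusion.

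**The concern.** A Cox model needs either the time of the event or at least the correct order of event times. Here a patient who recovers on Day 10 and one who recovers on Day 50 are both first seen as recovered at Visit 1, between Day 53 and Day 59. If actual dates are used, their order in the partial likelihood is the order of their appointments, which can differ by up to 6 days for reasons unrelated to recovery. If nominal weeks are used, all events fall on a few tied values and the estimate depends on a software option that the plan does not name.

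The stake is how the result is interpreted. Section 8.1 says the study is meant to generate hypotheses for later studies. A hazard ratio that moves with the clinic calendar or the tie option is a poor input for that purpose. It also invites a reading as speed of recovery in the first 8 weeks, which no visit measures.

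**Working it through.** **Inputs from the documents.** 40 relapse patients per arm; recovery at 2 months of 40% (control) and 70% (D-asp); one-sided alpha 0.05; 80% power (Section 8.1). Visits at Weeks 8, 12 and 24, i.e. Days 56, 84 and 168, each ±3 days: Days 53–59, 81–87 and 165–171 (Section 5.1).

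**The plan's own figure.** Without continuity correction, n = [1.645·√(2·0.55·0.45) + 0.842·√(0.4·0.6 + 0.7·0.3)]² / 0.3² ≈ 33 per arm. With the continuity correction it is 40 per arm, which reproduces the stated number. The plan gives no event count, hazard ratio (HR) or power for the Cox model.

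**How many events share the first window.** At Week 8: 0.4·40 + 0.7·40 = 16 + 28 = 44 recovered. Assuming constant hazards, recovery by Week 24 is 1 − 0.6³ = 0.784 (control) and 1 − 0.3³ = 0.973 (D-asp), so 31.4 + 38.9 = 70.3 events. About 44/70.3 = 63% of all events are therefore dated to Days 53–59.

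**Case A: 16/40 versus 28/40 at Week 8, no later recoveries (illustration).**
- HR consistent with the intervals, under proportional hazards: ln(1 − 0.7)/ln(1 − 0.4) = (−1.204)/(−0.511) = 2.36.
- Cox on nominal weeks, Breslow ties: with one event time and equal arms the score equation is 28 = 44·θ/(1 + θ), so θ = 28/16 = 1.75. This is just the risk ratio.
- Cox on nominal weeks, Efron ties: 2.24 (95% CI 1.21 to 4.15).
- Cox on actual dates, redrawing only the appointment days uniformly within ±3 days, 1,000 times: median 2.14 (Breslow) or 2.24 (Efron). The central 95% under Efron is 1.95 to 2.55, from identical patient outcomes.

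**Case B: later recoveries added** (16, 21 and 31 control versus 28, 33 and 39 D-asp recovered by Weeks 8, 12 and 24).
- Nominal weeks: 1.76 (Breslow), 2.23 (Efron).
- Redrawn dates, Efron: median 2.13, central 95% 1.74 to 2.64, extremes 1.55 and 2.99.
- Grouped-time complementary log-log model on the three intervals: 2.40, the same for every redraw because it does not use the dates.

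**Repeated sampling.** 500 simulated trials of 40 per arm; constant hazards with true HR 2.36; uniform visit dates; no dropout:

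| Analysis | Mean HR (geometric) | Power, two-sided 5% |
|---|---|---|
| Cox, exact times (not observable here) | 2.37 | 93% |
| Cox, actual visit dates, Efron | 2.15 | 87% |
| Cox, nominal weeks, Breslow | 1.76 | 72% |
| Cox, nominal weeks, Efron | 2.24 | 91% |
| Grouped-time complementary log-log | 2.43 | 92% |

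With no treatment effect and visit dates unrelated to arm, Cox on actual dates rejected in 3.6% of trials. Monte Carlo error is about 1 to 2 points.

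**The case against.** The best defence is that little depends on this model. It is the second of two exploratory analyses, no objective or listed endpoint concerns speed of recovery, and the Week 8, 12 and 24 comparisons of proportions do not use it. That stands, and it limits the weight of the point.

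Secondly, Section 8.4.1 calls the methods an outline and defers full detail to an SAP before database lock. Tie handling and event dating could be settled there. This defence is only partial: Section 8.4.2 already commits to a Cox model with right-censoring alone, so the SAP would have to depart from it deliberately.

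Thirdly, the low figure of 1.75 requires Breslow ties on nominal weeks, which the plan does not prescribe. Nominal weeks with Efron ties come close to the grouped-time model (2.23 against 2.40 in Case B; power 91% against 92%), and the gap is small beside the sampling error at 40 per arm. This also stands. Naming Efron ties on nominal visits would remove most of the problem, and 1.75 should be read as the worst case.

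A reader might infer three stronger things. One is that appointment dates alone decide the recorded time. They do not: clinical status decides the interval, and dates decide only the order within a window. Another is that disability is scored at three visits only, but the ET visit is also scored, although it is one more appointment and not a recovery date. The third is that the false-positive rate is inflated. In simulation that happened only when one arm's visits were assumed to run 1 or 2 days earlier (9.8% and 18.6% rejections), and the blinded design in Section 6.10 gives no reason to expect it.

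**Conclusion.** The point holds for the exploratory Cox analysis. Recovery is interval-censored, and the stated method does not allow for this. For the same recoveries in Case A, the reported HR could be 1.75 (worst case), 2.24, or about 1.95 to 2.55 depending on the appointment days, against 2.36 from the intervals. The harm is attenuation and arbitrary variation. The documents do not support a claim that the primary result is compromised: the Week 8 chi-square test does not use these times. Nor do they support a claim of type I error inflation while visit dates are blinded and non-differential.

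The HRs rest on the plan's 40% and 70%. Case A assumes no later recoveries; Case B and the simulations use constant hazards. Dates are drawn uniformly within the window and there is no dropout, since the documents give no dropout rate.

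**What to change.** In the SAP, replace the Cox model with a grouped-time proportional hazards model: binary regression on person-interval records with a complementary log-log link, terms for Day 0–Week 8, Weeks 8–12 and Weeks 12–24, treatment and the planned covariates. It targets the same hazard ratio and needs neither appointment dates nor a tie method.

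Two rules must be written with it:
- **Time origin.** State whether time runs from first dose (Section 5.1) or relapse onset (Section 5.2).
- **ET scores.** State how they are assigned. For example, a recovery first seen at ET counts in the interval in which the ET visit falls, and a patient not recovered at ET is censored at the last completed interval. Because that example counts ET recoveries but not ET non-recoveries in the same interval, tabulate ET cases by arm.

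Report the result as exploratory recovery by visit interval, with no claim about speed of recovery within the first 8 weeks.

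The cost is slightly more SAP work and no day-level estimate of time to recovery, which the schedule could not have supported. No new data, visits or patients are needed.

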5.5 Criteria for Subject Withdrawal

5.5.1 Withdrawal from Study Therapy

A patient must be withdrawn from IP if any of the following occur:

- Patient withdraws consent;
- Patient is lost to follow up;
- Participation in another clinical study;
- Occurrence of an exclusion criterion which is clinically relevant and affects the patient's safety, if discontinuation is considered necessary by the Investigator and/or Sponsor;
- Therapeutic failure requiring urgent additional drug;
- Any events that unacceptably endanger the safety of the patient;
- Occurrence of adverse events, if discontinuation of study drug is desired or considered necessary by the Investigator and/or the patient;
- Occurrence of pregnancy;

- Serious intercurrent illness or significant worsening of intercurrent illness;
- MS-related neurological events requiring steroid treatment (in this case, an ET visit will be conducted, during which a blood sample will be taken before the start of the steroid treatment);
- Patients without relapse at entry in the study that will relapse during the 24-week treatment phase.

If a patient prematurely withdraws from the IP at any time during the study, he/she will undergo all assessments requested at the ET visit ([Section 7.1](#)) as soon as possible after his/her last injection. In any case, the appropriate electronic Case Report Form (e-CRF) section including the reason(s) for withdrawal from the IP must be completed.

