8.1 Sample Size

The primary study endpoint in the part of the study focused on relapsed patients is defined as the proportion of patients who, following a disease relapse associated with a worsening in their MS-related disability, return to baseline status within 8 weeks. Disability will be assessed through the Functional Systems Scores of the EDSS (Visual, Brainstem, Pyramidal, Cerebellar, Sensory, Bowel/Bladder and Ambulation score).

Available data from observational studies (Hirst et al, 2012) indicate that approximately 50% of the patients return to baseline EDSS within 2 months with standard treatments. Based on the fact that usually, in clinical studies where a rigid intention-to-treat (ITT) approach is used, a lower rate of responses/recoveries is observed as compared to observational studies, the expected rate of recovery at 2 months in the control group is set at 40%. With 40 patients per arm the study will be able to detect with 80% power, at the 0.05 alpha level (1-sided), an increase in the proportion of recovery at 2-months from 40% to 70%. The 1-sided significance level is justified by the exploratory nature of this study, aimed at generating study hypotheses to be tested in subsequent studies.

A total of 120 patients will be randomised to include the 40 RR-MS patients without relapses. This subgroup of patients without relapse has been included to assess whether D-Aspartate enhances LTP induction, by means of TMS

Refer to Section 6.3 for procedures of randomisation.

Eligible patients at the end of the screening period will be randomised in a 1:1 ratio to D-asp or placebo. Randomisation will be stratified according to age (<30 years vs. \geq 30 years) and site location (Rome+Naples+ Pozzilli vs. the other sites).

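### The exploratory time-to-recovery Cox model censors patients withdrawn unrecovered for failure before Week 8, so its hazard ratio can shift when early failure occurs

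*Combined protocol and SAP*

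**What the plan says.** The primary analysis is a chi-square comparison of the proportions recovered at Week 8 (section 8.4.2). The same section, and the synopsis, add two analyses labelled exploratory: a logistic regression and a Cox model of time to recovery. The censoring rule for the Cox model is one sentence: "Patients not recovered will be censored at last observation". It draws no distinction by reason for leaving, and no competing-event rule or sensitivity analysis is given for this model.

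Section 5.5.1 lists the reasons for which a patient must stop study product. Two bear on recovery: "Therapeutic failure requiring urgent additional drug" and "MS-related neurological events requiring steroid treatment (in this case, an ET visit will be conducted". Section 6.5.2 goes further for prohibited drugs, which include steroids outside the protocol course: a patient who receives one should leave the study.

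Recovery can be scored at Weeks 8, 12 and 24 (section 5.1, Table 1). The early termination (ET) visit repeats the Week 24 procedures, including the EDSS (section 7.1). The schedule shows nothing after ET.

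Section 8.3 places the efficacy analysis in the ITT population. Section 8.4.1 describes the methods as an outline and leaves full detail to a later SAP.

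**The concern.** Censoring in a Cox model, read as a comparison of how fast the arms recover, treats a censored patient as having the same later chance of recovery as comparable patients still followed. That is hard to defend for someone who left because treatment failed.

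The timing makes it matter more. Week 8 is the first scheduled assessment and the visit at which the plan expects most recoveries. A patient withdrawn unrecovered before then is censored at about the ET date and adds nothing to the Week 8 comparison. Removing such patients raises the apparent Week 8 recovery rate in the arm they came from. The arm with more early failures can then look faster to recover, and the hazard ratio can disagree with the Week 8 proportions reported beside it for a reason that has nothing to do with recovery.

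**Working it through.** **1. The plan's own figure.** Section 8.1 states "With 40 patients per arm the study will be able to detect with 80% power", and gives the test level and effect as "at the 0.05 alpha level (1-sided), an increase in the proportion of recovery at 2-months from 40% to 70"%. Allocation is 1:1. With z = 1.645 and 0.842 and mean proportion 0.55:

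- Uncorrected: n = (1.645·√(2·0.55·0.45) + 0.842·√(0.24 + 0.21))² / 0.30² = 32.9, so 33 per arm.
- Continuity-corrected: (32.9/4)·(1 + √(1 + 4/(32.9·0.30)))² = 39.3, so 40 per arm.

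The 40 per arm is reproduced with the continuity correction. The documents give no figure for the Cox model.

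**2. Inputs for the Cox check.**

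- Week 8 recovery, as a share of all randomised relapse patients: 40% placebo, 70% D-asp (section 8.1).
- Recovery by Weeks 12 and 24: 45% and 50% placebo, 75% and 78% D-asp. *Assumed.*
- Patients withdrawn unrecovered before Week 8 for failure: 5% to 20% per arm. *Assumed.* Section 8.1 gives no withdrawal rate. It lowers the control rate from 50% to 40% on a general ITT argument, which would equal 20% of otherwise recovering patients (10/50) if such withdrawals explained all of it.

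**3. Effect on the Week 8 risk set.** Risk-set recovery = recovered / (1 − early failures).

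- 20% placebo, 5% D-asp: 40/80 = 50.0% against 70/95 = 73.7%.
- 5% placebo, 20% D-asp: 40/95 = 42.1% against 70/80 = 87.5%.

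With failures kept at risk, both cases stay at 40% against 70%.

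**4. Hazard ratio.** Let R be cumulative recovery and w the early-failure fraction in an arm. The risk set at each visit is 1 − R(previous visit) with failures kept, and 1 − R(previous visit) − w under the written rule. The large-sample Cox estimate h (Efron ties) solves

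Σ over visits of { d_T − d · mean over f in (0,1) of [ (n_T − f·d_T)·h / ((n_C − f·d_C) + (n_T − f·d_T)·h) ] } = 0,

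where d and n are events and numbers at risk, T is D-asp and C is placebo. For example, at 10% in both arms the placebo risk sets are 0.90, 0.50, 0.45 and the D-asp risk sets 0.90, 0.20, 0.15, against 1, 0.60, 0.55 and 1, 0.30, 0.25 with failures kept.

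| Early failure, placebo / D-asp | HR, written rule | HR, failures kept |
|---|---|---|
| Design rates, 5% / 5% | 2.26 | 2.17 |
| Design rates, 10% / 10% | 2.38 | 2.17 |
| Design rates, 15% / 15% | 2.57 | 2.17 |
| Design rates, 20% / 5% | 1.76 | 2.17 |
| Design rates, 5% / 20% | 3.74 | 2.17 |
| Equal recovery (40/45/50%), equal failure | 1.00 | 1.00 |
| Equal recovery, 20% / 5% | 0.77 | 1.00 |
| Equal recovery, 5% / 20% | 1.29 | 1.00 |

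**5. Scale.** In a simulation at 40 per arm with slightly different later recovery rates (48/55% and 75/80%), the standard error of the log hazard ratio was about 0.28. On that scale the 10% / 10% case is a shift of ln(2.38/2.17)/0.28 = 0.33 standard errors, and the 20% / 5% case ln(1.76/2.17)/0.28 = −0.75.

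**6. Simulation at 40 per arm, 1,500 runs.** With equal recovery and 5% / 20% early failure, the one-sided 5% test rejected in about 20% of trials under the written rule and 4.7% with failures kept (two-sided: 12.7% and 4.4%). With 20% / 5% at the design rates, one-sided power was 63% and 89%.

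**7. Later withdrawals.** If the same withdrawals fall between Weeks 8 and 12, the hazard ratio is 2.27 (10% / 10%), 2.09 (20% / 5%) or 2.65 (5% / 20%) against 2.17, and 0.93 to 1.07 under equal recovery. Those patients have already counted as unrecovered at Week 8.

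**The case against.** The strongest reply is that censoring competing events in a Cox model estimates a cause-specific hazard ratio, a standard quantity that needs no assumption about what withdrawn patients would have done. On that view the table shows the gap between two estimands, not an error. This stands only in part. Stopping study product does not make recovery impossible, as death would, so the cause-specific reading does not fit cleanly. Nor does section 8.4.2 say that it wants one. A reader shown this hazard ratio next to the Week 8 proportions will take it as relative speed of recovery.

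Other objections hold and limit the point:

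- The model is exploratory. The robustness check that section 8.3 names for the primary endpoint is the per-protocol repeat, and no stated decision depends on this hazard ratio.
- Stopping study product (5.5.1) is not the same as leaving the study (5.5.2). Section 6.5.2 ends participation only if the added drug is prohibited. In practice ET is still normally the last observation, because no later visit is scheduled.
- Whether a new MS event is failure to recover from the index relapse is an estimand choice that the documents do not make. The 30-day stability requirement in the relapse definition (section 5.3) also narrows the window before Week 8, although 5.5.1 is worded more broadly.
- The largest figures are extreme. With 78% of D-asp patients recovered by Week 24, a 20% early-failure rate makes 20 of the 22 in 100 non-recoverers early failures.
- A patient back to baseline at an early ET visit would count as an early event. That was not modelled, so no size is claimed for it.
- A later SAP is to hold full details. But this is a stated rule, which a SAP would be expected to carry forward unless it is changed.

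**Conclusion.** The point holds in limited form. The rule treats outcome-related withdrawal as uninformative, and unrecovered failures before Week 8 contribute nothing to the Week 8 comparison in this model. The resulting shift is nil when recovery and early failure are both equal across arms, and modest when D-asp works and early failure is equal. It can go in either direction when early failure differs, including an apparent benefit when recovery is the same. It is smaller for withdrawals after Week 8. All sizes rest on assumed failure rates and assumed Week 12 and 24 recovery.

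Three stronger readings are tempting, and the documents do not support them:

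- *The primary result is biased.* The chi-square test on Week 8 proportions does not use this censoring rule.
- *All failures vanish before any assessment, so the hazard ratio is always distorted.* Only those withdrawn before Week 8 leave before the first scheduled assessment, and the equal-arm case shows no shift.
- *The rule breaks the ITT principle.* Section 8.3 defines ITT by who is included, and censored patients remain included. The remark in 8.1 that "in clinical studies where a rigid intention-to-treat (ITT) approach is used, a lower rate of responses/recoveries is observed" supports the planning rate for the 2-month proportion ("the expected rate of recovery at 2 months in the control group is set at 40"%), not this model.

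This is a cheap improvement, of low priority because the model is exploratory.

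**What to change.** Before unblinding, amend section 8.4.2, the synopsis and the SAP along these lines:

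*In the time-to-recovery analysis, patients withdrawn unrecovered for therapeutic failure requiring an additional drug remain in the risk set as not recovered to Week 24. The cumulative incidence of recovery will be reported by arm. A sensitivity analysis will censor all unrecovered patients at last observation.*

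State in the same place whether an MS event requiring steroids is handled the same way, and show the result both ways. Tabulate withdrawals by arm, reason and timing relative to Week 8, so that a reader can judge whether the two analyses could differ.

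The cost is a few sentences and one more model run; section 5.5.1 already has the withdrawal reason recorded in the e-CRF. The new hazard ratio takes a subdistribution (composite) meaning: it counts any unobserved recovery after ET as non-recovery, and it may be less favourable than the present one. No clinical rule changes.
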